The primary inhibitor of kallikrein in plasma is the *SERPING1* gene product, C1 esterase inhibitor (C1 INH) (Cicardi and Johnston 2012). C1 INH is a serine protease inhibitor (serpin) that normally prevents uncontrolled contact activation and BK production by covalently binding to and inactivating kallikrein (Patston, Gettins et al. 1991). Patients with HAE have mutations in the regulatory or coding regions of the C1 INH gene that result in either a failure to produce C1 INH or the production of nonfunctional C1 INH (Pappalardo, Cicardi et al. 2000). The amount of functional C1 INH produced by the unaffected allele is insufficient to control serine protease activity, including that of kallikrein, that is induced by even asymptomatic levels of vascular endothelial contact activation (Cicardi and Johnston 2012). As a result, even when a patient does not experience any symptoms, plasma HK levels may be lower than normal and BK is detectable (Cugno, Hack et al. 1993, Nussberger, Cugno et al. 1998, Kaplan, Joseph et al. 2002, Nussberger, Cugno et al. 2002, Suffritti, Zanichelli et al. 2014). During symptomatic attacks, which may be triggered by trauma, infection, changes in hormone levels (e.g., with oral contraceptive use or with the menstrual cycle), or emotional stress, kallikrein activation, HK cleavage and BK production increase, and circulating BK levels are dramatically elevated (Cugno, Nussberger et al. 2003, Bork, Meng et al. 2006, Cicardi and Johnston 2012, Martello, Woytowish et al. 2012).

The effective management of HAE involves the prevention and/or treatment of symptomatic attacks (Cicardi, Bork et al. 2012). Kallikrein is a proven target in the treatment of HAE. As noted above, C1 INH is a covalent kallikrein inhibitor, and plasma-derived purified C1 INH (Cinryze®, Berinert®) and a human recombinant C1 INH (Ruconest®) are licensed for the treatment of HAE attacks in the European Union (EU). In the United States (US), Berinert® and Ruconest® are licensed for this indication. Ecallantide is an engineered recombinant protein noncovalent binding kallikrein inhibitor with homology to tissue factor pathway inhibitor and is licensed in the US for treatment of acute attacks of HAE by subcutaneous injection (Martello, Woytowish et al. 2012, Riedl 2012). Administration of ecallantide is associated with an approximately 4% rate of anaphylaxis.

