Icatibant (Firazyr®) is also an attack medication option for most patients in the US and EU. Icatibant is a subcutaneously-administered synthetic peptide that works distinctly from the other HAE treatments in that it functions as a bradykinin B2 receptor antagonist.

In the EU and the US, licensed therapy for prevention of HAE attacks is limited to a purified plasma-derived C1 INH (Cinryze®) administered intravenously every 3 to 4 days (STN125267). Oral attenuated androgens such as danazol are also licensed for prevention of HAE attacks in some countries. While administration of androgens is convenient, unacceptable adverse effects (including androgenic hormonal effects [masculinization], intracranial hypertension and risk of hepatocellular adenoma/carcinoma) and contraindications (including pregnancy) limit their clinical use (Maurer and Magerl 2011, Cicardi, Bork et al. 2012).

A Phase 2, double-blind, placebo-controlled study (Study BCX4161-203 [OPuS-1]) in subjects with HAE confirmed that inhibition of plasma kallikrein by an oral prophylactic treatment can significantly reduce attack rates. In that study, subjects with high attack rates (>1 week) were treated with avoralstat (BCX4161), a potent, small-molecule inhibitor of human plasma kallikrein discovered at BioCryst Pharmaceuticals, Inc (BioCryst). Overall, avoralstat was shown to be efficacious, reducing attacks in most subjects (88%), irrespective of the attack definition (subject-reported, adjudicated and treated) and was generally safe and well-tolerated.

In a subsequent Phase 3, 12-week, parallel-group study of avoralstat (OPuS-2) as prophylaxis against HAE attacks, avoralstat did not reduce the rate of attacks relative to placebo treatment. The failure of this study to demonstrate a treatment difference is likely related to: the limiting physicochemical and pharmacokinetic properties of avoralstat (low solubility and half-life); difficulty in adhering to an administration schedule requiring dosing on an empty stomach three times per day; and inhibition of plasma kallikrein that was neither maximal nor sustained across a dosing interval. Further investigations of either novel oral kallikrein inhibitors that do not suffer from those limitations, or novel avoralstat formulations that overcome the limitations of the formulation studied to date, are warranted.

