#### 5.4.1. Rationale for Study Drug Doses

##### 5.4.1.1. Rationale for Target Concentrations Proposed as Efficacious

[figure not shown]
In healthy subjects in Study BCX7353-101, inhibition of plasma kallikrein was highly correlated with plasma BCX7353 concentrations ( $r = 0.92$ ). Therefore, sustaining BCX7353 concentrations near or greater than a target level over a dosing interval is hypothesized to reduce attacks of HAE in subjects with little or no functional C1 INH, the endogenous inhibitor of kallikrein and ultimately, bradykinin production.

Trough concentrations expected to be efficacious were determined on the basis of C1 INH plasma concentrations in healthy subjects and HAE patients and the relative potency of C1 INH and BCX7353 against plasma kallikrein determined in vitro. The underlying hypothesis is that restoring normal levels of kallikrein inhibitory activity will restore a normal phenotype and eliminate angioedema attacks in patients with HAE.

The original rationale for the calculation of efficacious target concentrations for this protocol was as follows: In the plasma kallikrein inhibition assay using HAE patient plasma, the  $EC_{50}$  of C1 INH was measured to be 213 nM and for BCX7353 was 15.9 nM, a 13.4-fold potency difference. The lower limit of the normal range (LLN) of C1 INH is 1680 nM; therefore, the LLN for C1 INH corresponds to a BCX7353 concentration of 125 nM, or 71 ng/mL (approximately  $8 \times EC_{50}$ ). If the BCX7353  $C_{tau}$  could be maintained above 71 ng/mL, total plasma kallikrein inhibitory activity would be in the normal range. This level of BCX7353 would be sufficient to replace normal function in HAE patients who have zero functional C1 INH. The average patient with HAE has functional C1 INH levels of about 30% of the normal mean (720 nM). In the average patient, the difference between this level and the LLN of C1 INH is 960 nM, which corresponds to about 73 nM or 41 ng/mL (approximately  $4 \times EC_{50}$ ) of BCX7353. In summary, maintaining  $C_{tau}$  at either  $\geq 41$  ng/mL or  $\geq 71$  ng/mL ( $4 - 8 \times EC_{50}$ ) should restore the normal phenotype in the average HAE patient, and most HAE patients, respectively.

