Since this protocol was initiated, newly available data suggest that a lower target concentration range of BCX7353 may be efficacious. Results of a Phase 3 blinded randomized 2-period cross-over study of a subcutaneous formulation of C1INH (CSL830) (COMPACT study) were recently reported. This study demonstrated an approximately 89-95% reduction in HAE attacks during the C1INH treatment period in patients with a qualifying minimum attack rate of at least 2 attacks per month at entry and an on-study attack rate of 3.6-4.0 attacks per month in the placebo period (Zuraw et al, 2016). An estimated exposure-response analysis of the mean trough C1INH level from this study indicated that the observed clinical responses correlated with C1INH trough levels of approximately 5.3 – 6.3 fold  $EC_{50}$  of C1INH on plasma kallikrein (210 nM) in the same assay as used to estimate the  $EC_{50}$  of BCX7353 on the same target enzyme [Figure 1](#). Baseline mean levels of endogenous C1INH in this population were reported to be at approximately 25.4% of normal mean ( $\sim 13.1 \times EC_{50}$ ), ie equivalent to approximately  $3.3 \times EC_{50}$ . Thus, high levels of efficacy were achieved in these severely affected HAE patients with the addition of exogenous C1INH equivalent to 2-3  $\times EC_{50}$  at trough. These data support a rationale that doses of BCX7353 resulting in a trough level of 2-3  $\times EC_{50}$  may also be efficacious, on a background mean level of endogenous C1INH of approximately  $3.3 \times EC_{50}$ .

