### **9.7.1. Prohibited Medications**

The following medications are prohibited in advance of screening through completion of the study given the potential for modulation of HAE attacks and/or exacerbation of HAE:

1. Use of C1 INH, androgens, or tranexamic acid for prophylaxis of HAE attacks within the 7 days prior to the screening visit or initiation during the study. Androgen use is not permitted at any time during the study. Use of a C1 INH therapy for treatment of attacks is not excluded at any time.
2. Use of an estrogen-containing hormonal contraceptive within 60 days of the screening visit or initiation during the study.
3. Initiation of a progesterone-containing hormonal contraceptive within 60 days of the screening visit or initiation during the study. Progesterone eluding IUDs may be placed at any time. Conversion from an oral progesterone contraceptive that inhibits ovulation to an injectable or implantable progesterone contraceptive is allowed up to 1 week prior to study drug initiation.
4. Use of an angiotensin-converting enzyme inhibitor at screening or initiation during the study.

The following are prohibited medications based upon nonclinical data generated with BCX7353:

1. Daily use of a medication that is clinically known to induce or inhibit drug transporters P-gp or BCRP 7 days prior to Day 1 or initiation during the study.

An updated list of such medications can be found at:  
<http://dbts.ucsf.edu/fdatransportal/transporters/ABCB1/> and  
<http://dbts.ucsf.edu/fdatransportal/transporters/ABCG2/>; see *clinical drug-drug interactions*, *Interacting Drug* column.

2. Daily use of a medication that primarily relies upon BCRP or P-gp transport proteins for systemic disposition 7 days prior to Day 1 or initiation during the study.

An updated list of such medications can be found at:  
<http://dbts.ucsf.edu/fdatransportal/transporters/ABCB1/> and  
<http://dbts.ucsf.edu/fdatransportal/transporters/ABCG2/>; see *clinical drug-drug interactions*, *Affected Drug* column.

3. Use of a medication that is clinically known or possibly to prolong the QT interval 7 days prior to Day 1 or initiation during the study.

Medications falling into the *drugs with a known risk of torsades de pointes*, *drugs with a possible risk of torsades de pointes* are listed at:  
<https://www.crediblemeds.org/index.php/?CID=328> (please note this website requires registration)

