#### **2.2.2. Secondary Endpoints**

- Safety and tolerability of BCX7353 as assessed by adverse events (AEs), clinical laboratory tests, electrocardiograms (ECG), vital signs, and physical exam findings
- Number of attacks requiring attack medication (Medications recorded on Diary page to treat HAE attack include Cinryze, Berinert, Firazyr, Ruconest, Tranexamic acid and Kalbitor)
- Duration of attacks
- Severity of attacks
- Attack onset relative to the time of last dose of study drug
- Discontinuations due to lack of efficacy
- Symptoms and anatomical locations of attacks
- Number of emergency room visits and/or hospitalizations

- Quality of life scales, as measured by the Angioedema Quality of life (AE-QoL) and Depression, Anxiety, Stress Scales (DASS)
- BCX7353 steady-state pharmacokinetic (PK) parameters including  $C_{\max}$ ,  $C_{\tau}$ ,  $T_{\max}$ ,  $AUC_{\tau}$ ,  $AUC_{0-t}$ , half-life,  $\lambda$ ,  $V_d/F$ , and  $CL/F$
- *Ex-vivo* kallikrein inhibition
- Cleaved high-molecular-weight kininogen (HK) and C1INH functional level values and change from baseline

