### **6.6. Pharmacodynamic Populations**

#### **6.6.1. Plasma Kallikrein Inhibition**

The PD population for plasma kallikrein inhibition (KKI) will include all subjects for whom at least 1 pre- and post-dose plasma kallikrein inhibition result can be estimated. This population will be used for all analyses of plasma kallikrein inhibition.

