## 14. PHARMACODYNAMIC ANALYSES

### 14.1. Kallikrein Inhibition, Cleaved HK Fragments, and C1 INH

On-treatment plasma kallikrein inhibition data (assessed with and without stimulation by ellagic acid) will be expressed as percent inhibition compared to subject baseline activity. Ex vivo plasma kallikrein activity will be listed by subject, treatment, day, and time and summarized separately by treatment, day, and time. Descriptive statistics will be reported. Mean and individual plasma kallikrein inhibition versus time profiles will be plotted by treatment group. Plasma kallikrein inhibition data from Day 14 or Day 28 will be combined by treatment group for analysis. The difference between each active treatment group vs placebo and between active doses in plasma kallikrein inhibition will be analyzed using a repeated measures analysis of variance with time, treatment and time by treatment as fixed effects. Subject will be fitted as a random effect in the model. The point estimates and corresponding 95% confidence interval (CI) for treatment differences will be calculated at each time point.

Cleaved HK fragments and C1 INH functional levels and absolute change from baseline will be summarized by treatment group. The HK end of treatment /Baseline ratio will also be listed and summarized by treatment group. The difference between each active treatment group and placebo and the pairwise difference between active doses in C1inh Change from baseline, cleaved HK change from baseline and HK end of treatment /Baseline ratio will be analyzed using ANOVA with treatment as fixed effects. Baseline value will be included as a covariate. The point estimates and corresponding 95% confidence interval (CI) for treatment differences will be calculated for each comparison.

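### The secondary PD analyses take no account of C1 INH rescue given shortly before a sample; a derived flag and a pre-specified repeat analysis would show whether it matters

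*SAP*

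**What the plan says.** **Rescue.** Protocol 9.7.1 states: "Use of a C1 INH therapy for treatment of attacks is not excluded at any time". SAP 2.2.2 lists what the diary captures: "Medications recorded on Diary page to treat HAE attack include Cinryze, Berinert, Firazyr, Ruconest, Tranexamic acid and Kalbitor". Protocol 5.1 identifies three of these six (Cinryze, Berinert, Ruconest) as C1 INH products.

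**Link to the PD measures.** Protocol 5.1 says that "C1 INH is a covalent kallikrein inhibitor". Protocol 5.4.1.1 reports an EC50 of 213 nM for C1 INH, obtained "In the plasma kallikrein inhibition assay using HAE patient plasma". C1 INH functional level is itself a PD endpoint.

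**Analyses.** Under SAP 14.1, kallikrein inhibition is "expressed as percent inhibition compared to subject baseline activity". It compares arms with a repeated-measures model containing time, treatment, their interaction and a random subject effect. Change in C1 INH and in cleaved HK is compared with a treatment term and the baseline value as covariate. SAP 14.2 adds exposure-response analyses and a comparison of HK and C1 INH by attack-free status among actively treated subjects. The table list in SAP 16 also plans kallikrein inhibition by attack-free response.

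**Who and what is included.** SAP 6.6.1 admits any subject with an estimable pre- and post-dose result and adds: "This population will be used for all analyses of plasma kallikrein inhibition". SAP 6.6.2 does the same for C1 INH and cleaved HK. SAP 10.3 takes the last pre-dose value as baseline, with no condition on recent rescue.

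**The concern.** A C1 INH dose taken shortly before a PD draw can raise the measured C1 INH function and add kallikrein inhibition that the study drug did not cause. Three consequences follow if the plan is run as written.

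- **Arm contrasts.** On-treatment rescue follows attacks, and attacks are more frequent on placebo. Contamination therefore differs by arm. It pushes C1 INH function upward on placebo and tends to shrink the active-minus-placebo difference in kallikrein inhibition.
- **Attack-free comparison.** Among treated subjects, those with attacks are the ones who take on-treatment rescue. A difference in C1 INH function by attack-free status may show only who was treated for an attack.
- **Baseline.** C1 INH before the Day 1 sample makes later inhibition look smaller. Randomisation balances this in expectation, so it mainly adds noise and attenuation in all arms.

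C1 INH function is scheduled for every subject only on Day 1 and Day 29. One affected sample therefore decides a subject's change score, in active groups that numbered 6, 7 and 18 at the interim.

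**Working it through.** **1. Search for a rule.** Rescue timing does not appear in the PD populations (SAP 6.6), missing-data handling (10.1), baseline (10.3), multiple measurements (10.5), assessment windows (10.7) or the PD and PK/PD analyses (14.1, 14.2). It is also absent from Protocol 11.1.14 and 13.2.7. The nearest parallel is in SAP 10.2, which drops 24-hour PK samples taken after the next day's dose. The data for a rule do exist: Protocol 11.2.2 has subjects record treatments and their times, and SAP 12.1.4 already derives time from attack onset to first HAE medication.

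**2. How often a Day 29 sample could be affected.** Inputs from Protocol 5.3.3.3 are the placebo rate of 0.898 confirmed attacks per week and a reduction of 0.434 for all doses combined, so the active rate is 0.898 − 0.434 = 0.464. Assumptions not in the documents: attacks arrive at a constant rate, a share *f* = 0.25 to 0.75 is treated with C1 INH, and a dose matters for *w* days.

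Share affected = 1 − exp(−rate × *w*/7 × *f*)

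| *w* | *f* | Placebo | Active |
|---|---|---|---|
| 4 days | 0.25 | 1 − exp(−0.128) = 12% | 1 − exp(−0.066) = 6% |
| 4 days | 0.75 | 1 − exp(−0.385) = 32% | 1 − exp(−0.199) = 18% |
| 7 days | 0.25 | 1 − exp(−0.225) = 20% | 1 − exp(−0.116) = 11% |
| 7 days | 0.75 | 1 − exp(−0.674) = 49% | 1 − exp(−0.348) = 29% |

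For Day 1, the expected baseline of 1 attack per week (SAP 5) with *w* = 4 gives 1 − exp(−0.143) = 13% to 1 − exp(−0.429) = 35%, in every arm.

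**3. What one affected sample could look like (illustration only).** Protocol 5.4.1.1 puts endogenous C1 INH at 25.4% of about 13.1 x EC50. This reproduces: 0.254 × 13.1 = 3.33, against the stated 3.3. In the cited subcutaneous C1 INH prophylaxis study, "high levels of efficacy were achieved in these severely affected HAE patients with the addition of exogenous C1INH" at 2–3 x EC50 at trough.

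- C1 INH level: (3.3 + 2)/3.3 = 1.6 to (3.3 + 3)/3.3 = 1.9 times background.
- Kallikrein inhibition with no study drug, assuming additive inhibitors and slope 1: 1 − 4.3/6.3 = 32% to 1 − 4.3/7.3 = 41%.
- The same model for 125 mg at its mean trough of 4.63 x EC50 (Protocol Table 2), with no rescue: 1 − 4.3/8.93 = 52%. The observed figure is about 40% (Protocol 5.3.3.2).
- The same subject with an affected Day 1 sample: 1 − 6.3/8.93 = 29% to 1 − 7.3/8.93 = 18%.

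**4. Cost of excluding samples.** Dropping any Day 1/Day 29 pair with either sample within 7 days of a C1 INH dose would lose:

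- placebo: 1 − exp(−(1 + 0.898) × 0.25) = 38% to 1 − exp(−1.898 × 0.75) = 76%
- active: 1 − exp(−(1 + 0.464) × 0.25) = 31% to 1 − exp(−1.464 × 0.75) = 67%

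**The case against.** **The size is not established. This stands.** The documents give neither the share of attacks treated with C1 INH nor how long one acute dose persists. The phrase "administered intravenously every 3 to 4 days" in Protocol 5.1 describes prophylactic dosing and is not a duration of effect after rescue. Icatibant is a permitted alternative and acts at the B2 receptor (Protocol 5.1), so it would not contaminate samples in this way. The documents also do not say that the on-study exploratory ex-vivo assay is the one that yielded the C1 INH EC50. That weakens the kallikrein part, but not the C1 INH function part.

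**Interim data show no gross distortion. This partly stands.** With rescue unrestricted, Protocol 5.3.3.2 found inhibition in HAE subjects consistent with that in healthy subjects, and a correlation with exposure of 0.85. This is reassuring about the kallikrein data in treated subjects. It does not address C1 INH function or the attack-free comparison.

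**The SAP leaves room to act later.** SAP 11.2 provides a data review meeting and SAP 11.3 allows data-handling rules to be refined. Neither is a pre-specified rule, and Protocol 5.4.1.1 shows that unblinded data through Part 2 are already in hand.

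**Stronger readings that the documents do not support.**

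- A reader might infer that the 4x and 8x EC50 targets are distorted. SAP 13.2 fixes them at 35.8 and 71.6 ng/mL and applies them to BCX7353 concentrations, so a contaminated PD sample cannot move them. Protocol 5.4.1.3 does cite predicted kallikrein inhibition in its dose rationale, but it bases the Part 4 decision on PK, safety and efficacy.
- A reader might infer that rescue alone equals the 125 mg effect, because 32–41% resembles the observed 40–42%. That sets a modelled value beside an observed one. Like for like, the model gives 52% for 125 mg, and its inputs are prophylaxis troughs.
- A reader might want affected samples removed from the main analysis, using the 7-day look-back. In Protocol 9.7.1 that is a pre-screening rule on prophylaxis and not a PD washout. Removal could cost 31–76% of pairs and would condition on post-randomisation attacks.

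**Conclusion.** The gap is real and goes beyond missing detail. Followed as written, the plan lets C1 INH rescue enter the between-arm PD contrasts at different rates by arm, and confounds the attack-free comparison of C1 INH function. The case is strongest for C1 INH function, which needs no assay model. For kallikrein inhibition it rests on C1 INH acting in the on-study assay as it does in the assay of Protocol 5.4.1.1.

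The frequencies rest on the assumed C1 INH share, the assumed window and a constant attack rate. They use confirmed attacks, whereas rescue is taken for subject-reported ones. Whether the resulting bias is material cannot be judged from the documents.

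The reach is limited to secondary PD endpoints in a study with no formal hypotheses (Protocol 13.2.4). This is a minor point and a cheap improvement.

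**What to change.** In SAP 14.1 and 14.2:

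1. For every PD sample, including Day 1, derive the time since the last C1 INH dose from the diary product and administration time.
2. Keep the all-samples analysis as planned.
3. Pre-specify a repeat of the C1 INH, cleaved HK, kallikrein-inhibition, exposure-response and attack-free analyses without samples or baselines drawn within a stated window of a C1 INH dose. Windows of 4 and 7 days would serve, labelled as assumptions.
4. Report the number of flagged samples by arm and visit.
5. State that arm or attack-free differences in C1 INH function will be interpreted only alongside the repeat.

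The cost is one derived variable, a few sentences and some extra tables, with no new data and no change to the permitted use of rescue. The repeat will have small numbers, and its on-treatment exclusions depend on post-randomisation attacks. It is therefore a sensitivity analysis and not a replacement.

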### 14.2. Correlations of Dose or Drug Exposure with Pharmacodynamic Responses and Efficacy Outcomes

The following dose-response and exposure-response analyses of the relationships between pharmacokinetic, pharmacodynamic and efficacy measures will be explored using descriptive statistics, correlation assessment and model-based techniques as data permit:

- Correlation and exposure-response between plasma kallikrein inhibition and BCX7353 plasma concentrations
- Correlation and exposure-response between BCX7353 PK Parameters ( $C_{max}$ ,  $AUC_{tau}$ , mean  $C_{tau}$ ) and confirmed weekly HAE attack Rate
- Correlation between BCX7353 PK Parameters ( $C_{max}$ ,  $AUC_{tau}$ , mean  $C_{tau}$ ) and cleaved HK Change from baseline to the end of study and HK Follow-up/Baseline Ratio
- Correlation between the percent of plasma BCX7353 trough concentrations ( $C_{tau}$ ) above 4x and 8x kallikrein inhibition  $EC_{50}$  and confirmed attack rate

The correlation and exposure-response assessments will be presented graphically using a scatter plot along with the fitted regression line. Person correlation coefficient and p-value will be included on the plot.

- Plasma BCX7353 concentration, PK Parameters ( $C_{max}$ ,  $AUC_{tau}$ , mean  $C_{tau}$ ), and PD (HK, C1INH) data will be presented by attack free status

The PK and PD parameter will be summarized by subgroup based on attack free status for the subjects received the active BCX7353 dose. The between group difference will be estimate based on an ANCOVA model including fixed effect of subgroup. The qualifying attack rate will be included as a covariate.

- Comparison of confirmed attack rate between subgroup based on average plasma BCX7353 trough concentrations ( $C_{tau}$ ) above 4x and 8x kallikrein inhibition  $EC_{50}$  values

The confirmed attack rate will be summarized by subgroup based on the average plasma BCX7353 trough concentrations ( $C_{tau}$ ) for subjects received the active BCX7353 doses. The between group difference will be estimate based on an ANCOVA model including fixed effect of subgroup. The qualifying attack rate will be included as a covariate.

Additional PK-PD analysis may be explored as data permit.

